1.2.7 Rationale for pharmacokinetic, pharmacogenetic and neutrophil function assay

Since the clinical trial 17C0009 was open to accrual, an unexpected phenomenon has been observed on multiple occasions- neutropenia with quick onset and quick recovery. Per current protocol, the hematologic toxicities have been mainly attributed to TMZ which is known for the bone marrow toxicities, including thrombocytopenia, leukopenia, neutropenia and lymphopenia. The complete blood count (CBC) of more than one patient happened to be tested based on clinical needs at several occasions. In those tests, absolute neutrophil count (ANC) in some patients was found to be decreased significantly. Interestingly, the low ANC can be found to be recovered within 24-48 hours in most cases. In one case, patient was found to have grade 4 neutropenia within 24 hours after one dose Zotiraciclib (TG02) but recovered to grade 1 neutropenia 24 hours later. The quick onset and quick recovery suggested that the bone marrow dysfunction is unlikely to be the etiology for the neutropenia that was observed in these cases. In addition, in most cases where this transient neutropenia occurred, there were no decreases in lymphocytes, platelets and hemoglobin. Although there were no serious consequences, such as infection in these cases, study drug had to be discontinued. Without knowing the pathophysiology of this type of neutropenia, the study drug can be discontinued prematurely. On the other hand, patients will be at risk if the follow up lab tests are not scheduled appropriately. It would be important to understand the effect of Zotiraciclib (TG02) on neutrophil biology.

To analyze the neutrophil function after Zotiraciclib (TG02) administration, information from pharmacokinetic study is crucial. To further understand why this neutropenia only happened in a subgroup of patients but not all patients receiving Zotiraciclib (TG02), we will add pharmacogenetic study by analyzing the genomic DNA and assess genotype of the most relevant drug metabolizing enzymes and transporters (DMET).

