9. On cycle 1 day -3, collect following samples from patients in the **Phase 1 cohort expansion only**: PK studies (1 6mL green sodium heparin tube at following timepoints-pre-dose, 1hr, 2hr, 4hr, 12hr, 24hr, 48hr, and 72hr post-oral dose); PG studies (1 purple tube EDTA, 6mL, pre-dose) and neutrophil analysis (2 additional purple top EDTA, 6mL each for CBC/diff and neutrophil marker; and 1 additional heparinized green top tube, 6 mL for plasma isolation for monitoring neutrophil activation markers) at following timepoints- pre-dose, 1hr, 2hr, 4hr, 12hr, 24hr, 48hr, and 72hr post-oral dose). All effort will be made to collect samples at prescribed time points; missed timepoints or collections outside the window will be documented but not constitute a deviation.
10. Research sample will be collected for PK/PG study from patients enrolled to the **Post-Interim Analysis cohort** at the following timepoints: pre-dose, 1hr, 2hr, 4hr, 24hr, and 48hr post-oral dose. This will avoid the requirement for inpatient admission. The neutrophil sample will not be collected.
*+/- 3 business days

** Allowance for scheduling changes: Brief interruption and delay in the 28-day cycle may occasionally be required due to travel delays, airport closure, inclement weather, family responsibilities, security alerts and government holidays, etc. This can also extend to complications of disease not attributable to disease progression or protocol therapy. These delays will not be considered protocol deviation. However, any interruption more than 14 calendar days will not be permitted.

*** on days 2, 8, 14, 21, and 28 (+/- 2 days). The ProCTCAE data will not be collected from patients enrolled to the post-interim analysis cohort.

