5.1.4.1 Collection

- a. CBC with differential (a tube of 6 cc blood collected in purple top tube) will be done on cycle 1 day -3 at the following time points*: pre-dose, 1hr, 2hr, 4hr, 12hr, 24hr, 48hr, and 72hr post oral Zotiraciclib (TG02). Neutrophil morphology will be studied by using Cellavision program.
- b. Collect blood sample (6 cc of blood in heparinized green top tube) at the time of PK sample collection for plasma isolation for monitoring neutrophil activation markers.
- c. Collect (6 cc of blood in purple top tube with EDTA), fix and stain neutrophils at the same time points of the PK sample collection. Samples will be used for neutrophil cell surface markers including but not limited to CD11a, CD11b, CD11c, CD32, CD18, CD67, CD64, CD18, CD45, CD62L, CD63, 7D5.

* All effort will be made to collect samples at prescribed time points; missed timepoints or collections outside the window (+/- 30 minutes from the scheduled time) will be documented but not constitute a deviation.

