In phase I, for each arm, the maximum sample size of 24 patients will be used for dose finding. As there are 4 doses, on average at least 6 patients will be treated at the MTD. After the MTD is selected, cohort expansion will be conducted at the MTD until the total number of patients treated at the MTD reaches 18 patients (including the patients who have been treated in the dose-finding part). Thus, no more than 12 additional patients will be enrolled during the cohort expansion phase. Therefore, the maximum number of patients for phase I, including dose finding and cohort expansion, is 24+12=36 patients per treatment arm, and 72 in total for two treatment arms.

During the interim analysis of the Phase I study, we identified TG02 of 250 mg as the MTD in both Arm 1 and Arm 2. Cohort expansion was conducted independently at each of the MTD into treatment arms, and the PSF4 was found to be 38% in Arm 1 and 25% in Arm 2. Therefore, based on the preplanned analysis, the DD TMZ dosing schedule is considered a “winner” to be used in Phase II study. However, a better PFS was found in patients who received TG02 at dose level 0, compared to those received TG02 at dose level 1, which is MTD, in Arm 1, the winner arm, suggesting the lower dose with the scheduled TMZ may be sufficient if not more beneficial for patients with recurrent high grade astrocytoma. However, we cannot make the conclusion based on the small sample number in Arm 1 at dose level 0. Therefore, we would like to continue enrolling to the maximum, allow the additional 12 patients enrolled to be treated with TG02 at dose level 0 combined with dd TMZ.

We do not plan to change the study design. The primary endpoint is still toxicity. The objective is to add a small cohort expansion to better characterize the dose-toxicity relationship and obtain some preliminary efficacy readout to determine RP2D. If PFS4 month difference between MTD and (MTD-1) is less than 5%, select the lower dose, I.e., MTD-1, as the RP2D; otherwise select the MTD as RP2D.

There should not be safety concerns because additional patients will be treated with TG02 at a dose that is lower than the MTD that was identified previously.

The purpose for enrolling more patients is to further define a dosage not only safe but optimal for the patients before we move to Phase II study. Only AE and PFS4 will be recorded in these subjects.

10.2 PHASE II COMPONENT:

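### The 200 mg post-interim cohort lacks the serial post-dose blood counts taken in the 250 mg expansion, so the descriptive neutropenia comparison by dose is tilted toward 200 mg

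*Combined protocol and SAP*

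**What the plan says.** Section 10.1 reports that at the interim analysis "we identified TG02 of 250 mg as the MTD in both Arm 1 and Arm 2". It then extends enrolment in Arm 1 to "allow the additional 12 patients enrolled to be treated with TG02 at dose level 0 combined with dd TMZ". Toxicity stays the primary endpoint, and the stated aim begins: "The objective is to add a small cohort expansion to better characterize the dose-toxicity relationship". Only adverse events and PFS4 are to be recorded in these patients. The Statistical Analysis Plan text in 10.2 tabulates adverse events by grade and dose level.

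Section 1.2.7 explains why neutrophil sampling was added. Neutropenia of quick onset had been noticed on counts that happened to be taken for clinical reasons, with recovery in most cases within 24-48 hours. In one case the "patient was found to have grade 4 neutropenia within 24 hours after one dose Zotiraciclib (TG02) but recovered to grade 1 neutropenia" a day later.

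The response was serial sampling. Under 5.1.4.1, "CBC with differential (a tube of 6 cc blood collected in purple top tube) will be done on cycle 1 day -3", at pre-dose and at 1, 2, 4, 12, 24, 48 and 72 hours. Section 3.8, footnote 9, and the table in 5.1 limit this to the cohort expansion. For the post-interim cohort, footnote 10 of 3.8 keeps pharmacokinetic draws at pre-dose, 1, 2, 4, 24 and 48 hours but adds: "The neutrophil sample will not be collected". The footnote to the 5.1 table agrees.

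**The concern.** A cohort added to describe how toxicity changes with dose should measure that toxicity in the same way at both doses. Here the group at the higher dose includes patients watched hour by hour after the first dose. The group at the lower dose is watched only by routine counts that are not timed to a dose. For an episode lasting one or two days, that difference alone lowers the recorded frequency at 200 mg. A table of events by dose level could then show a dose-toxicity gradient that comes wholly or partly from the sampling schedule.

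The retained pharmacokinetic and pharmacogenetic samples are affected too. Section 5.1.3.1 intends to correlate plasma levels with toxicity, and 1.2.7 adds genotyping to explain why only some patients become neutropenic. At 200 mg there is no scheduled count at the times when those samples are drawn.

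**Working it through.** The plan states no figure for this comparison, so there is nothing to reproduce. The check has two parts.

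**Who has serial counts**

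- 250 mg, per arm: 18 patients in total, including those from dose finding (10.1). Dose finding stops once 12 patients have been treated at a dose, so at least 18 - 12 = 6 are expansion patients. The protocol allows no more than 12 expansion patients. So m = 6 to 12 of 18 are scheduled for the eight-point series. The actual number is not given.
- 200 mg: none. Dose-finding patients fall outside the expansion, and the post-interim cohort is expressly excluded.

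**What routine counts would find**

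Inputs from the documents: Zotiraciclib on days -3, 1, 12, 15 and 26 of cycle 1 (3.1.4); a routine count in week 2 and in week 4 (3.5.1).

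Assumptions: a susceptible patient has a low count on the two days after each dose; routine counts fall uniformly within days 8-14 and 22-28; the serial series detects every case.

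In week 2 the informative days are 13 and 14, and in week 4 they are 27 and 28, so each count hits with probability 2/7. Routine detection s is then:

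- one count only: s = 2/7 = 29%
- cycle 1, both counts: s = 1 - (5/7)² = 49%
- two cycles, four counts: s = 1 - (5/7)⁴ = 74%
- cycle 1, with the second count taken in the 72 hours before the next cycle (3.3.1.1), assumed uniform on days 26-28, so a 2/3 hit: s = 1 - (1/3)(5/7) = 76%

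With a true rate p at both doses, the detected rates are

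- 200 mg: p × s
- 250 mg, all 18: p × [m/18 + (1 - m/18) × s]
- gap: p × (m/18) × (1 - s)

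The gap is positive whenever s is below 1, so its direction does not depend on the assumed values.

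For p = 30% (assumed; the documents give no rate):

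| Routine detection s | 200 mg | 250 mg, m = 6 | 250 mg, m = 12 |
|---|---|---|---|
| 29% | 8.6% | 15.7% | 22.9% |
| 49% | 14.7% | 19.8% | 24.9% |
| 74% | 22.2% | 24.8% | 27.4% |
| 76% | 22.9% | 25.2% | 27.6% |
| 80% | 24.0% | 26.0% | 28.0% |

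At s = 49%, other true rates give 4.9% against 6.6-8.3% (p = 10%), 9.8% against 13.2-16.6% (p = 20%) and 19.6% against 26.4-33.2% (p = 40%).

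**The case against.** The case on the other side is substantial and limits the point in four ways.

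- **Dose selection.** A reader might infer that the bias helps to choose 200 mg for phase II. The rule in 10.1 does not support that: it takes the lower dose if PFS4 differs by less than 5% and the MTD otherwise. It has no toxicity term, so unequal counts cannot change its result.
- **Formal toxicity.** Under 3.1.3, grade 4 neutropenia is dose-limiting only if it lasts at least 5 days; the separate febrile criterion needs fever or infection. An episode that clears in 24-48 hours misses the duration criterion. One route remains: a cycle 1 hold, reduction or discontinuation counts as a DLT at the PI's discretion, and Table 11 calls for action on grade 3-4 hematologic findings. Section 1.2.7 says that drug had to be discontinued in such cases. Detection can therefore reach the DLT count, but only by that path.
- **Adverse events.** Section 6.1 makes a laboratory value an adverse event only under listed conditions, so a low research count does not automatically enter the table. The series also serves an exploratory objective (1.1.3.3), and no inferential comparison of neutropenia between doses is planned.
- **Size.** A reader might set 30% against 15%. That contrast treats all 250 mg patients as serially sampled and stops at cycle 1. It ignores the 250 mg dose-finding patients, the counts in later cycles and the count needed before the next cycle.

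A reader might also infer that safety at 200 mg goes untested. It does not: routine counts continue, and in phase I a grade 3 finding triggers repeat counts every 3 days (3.5.1). The reassurance in 10.1 rests on the dose lying below the MTD, not on the neutrophil series.

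None of this answers the remaining point: toxicity by dose is a stated deliverable of this cohort, and its neutropenia component is measured differently at the two doses without comment.

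**Conclusion.** The concern holds for the descriptive comparison of neutropenia between dose levels 0 and 1. Rapid, transient neutropenia is ascertained more closely at 250 mg, and the bias favours 200 mg. With an assumed true rate of 30% at both doses, the artificial gap is about 5-10 percentage points if routine counts detect 49% of cases, and about 3-5 points if they detect 74%. These sizes rest on the assumed rate, the two-day window after every dose, uniform timing of routine counts, full detection by the series and 6-12 serially sampled patients of 18. They concern detected low counts; recorded adverse events are affected only where 6.1 is met. The PFS4 rule for the phase II dose is untouched. This is a modest flaw that is cheap to correct.

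**What to change.** **Analysis wording.** In 10.1 and in the Statistical Analysis Plan text of 10.2, state that neutropenia is compared between dose levels 0 and 1 only on safety counts scheduled in both groups. List separately any finding seen only on the research counts from day -3 to 72 hours. This makes detection equal, though still incomplete, at the two doses. It does not undo any hold or reduction that a research count prompted, so those should be identified in the listing. The cost is wording only; the downside is that some research-only counts at 250 mg leave the between-dose table.

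**Optional sampling.** Add one EDTA tube for a count with differential at the pre-dose, 24-hour and 48-hour pharmacokinetic draws already kept for the post-interim cohort, and compare with the same three time points in expansion patients. The cost is one tube at three existing draws in up to 12 patients, with no extra visit or admission. If these counts detected every case (assumed), the chance of seeing none in 12 patients at a true rate of 20% would be 0.80¹² = 7%, against (1 - 0.20 × 0.49)¹² = 29% with cycle 1 routine counts alone. At a true rate of 30% the figures are 1.4% and 15%.

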1.2 BACKGROUND AND RATIONALE

1.2.1 Disease background

High grade astrocytomas include glioblastoma (GBM) [WHO grade IV] and anaplastic astrocytoma (AA), [WHO grade III]. Both are highly malignant and belong to gliomas. Gliomas

represent 80% of malignant CNS tumors. GBM accounts for 54% of gliomas and AA accounts for 7%.[\[1\]](#)

Histologically, GBM displays a high mitotic index, cellular pleomorphism, and extensive vascular proliferation or necrosis. They are characterized by their intrinsic heterogeneity, high morbidity and mortality. Despite aggressive multimodality treatment approach in surgery, radiation therapy and cytotoxic chemotherapies, the prognosis of patients with GBM remains poor with a median survival rate of less than 18 months.[\[2\]](#) Recurrent GBM has an even more dismal prognosis with a median overall survival of approximately 25 weeks. [\[3\]](#)

Anaplastic astrocytoma (AA) is classified by WHO as a grade III glioma, demonstrating a less aggressive behavior when comparing to GBM. AA frequently transforms to GBM. The treatment of recurrent AA is unsatisfying. Chemotherapy and re-operation for recurrent AA is of modest benefit and only bring short responses. Wong et al reported that a progression free survival rate at 6 months is 31% and the median progression free survival is only 13 weeks based on eight phase II clinical trials that included 150 patients with recurrent AA.[\[3\]](#) In the pivotal clinical trial that led to the accelerated FDA approval in 1999 for TMZ as the treatment of recurrent AA, the PFS6 and median overall survival were reported as 46% and 13.6 months respectively.[\[4\]](#)

[figure not shown]

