Once patients with glioblastoma have recurrent disease after standard treatment defined as concurrent radiation plus daily TMZ followed by 6-12 cycles of adjuvant TMZ (150-200 mg/m² days 1-5 of a 28-day cycle), the disease is typically less responsive to TMZ. This resistance has been attributed to an increase in the tumor intracellular concentration of the enzyme O6-methylguanine DNA methyltransferase (MGMT). It has been demonstrated that if the MGMT can be depleted, sensitivity to alkylating agents such as TMZ can be restored. A study by Tolcher and his colleagues demonstrated that there was a more pronounced depletion of MGMT in peripheral blood mononuclear cells (PBMCs) after dose-intense dosing schedule of TMZ.[39] Building on this data, many studies explored the use of alternative schedules. The most notable evaluated the 7-day on – 7-day off and a metronomic schedule that used daily continuous dosing of 50 mg/m² of TMZ.

Dose-dense schedule: In a prospective study, ninety adult patients with recurrent glioma were treated with TMZ at 150mg/m²/day on days 1-7 and 15-21.[40] PFS6 was reported to be 43.8% and one-year survival rate was 23%. In contrast, another study in a similar patient population reported a PFS6 of 10% and median overall survival was 21.6 weeks.[41] Both studies demonstrated good tolerance of the treatment.

Metronomic dosing: A study of recurrent glioma patients who received metronomic TMZ at 50mg/m² yielded a PFS6 of 23.9% and a 1-year survival rate of 27.3% in recurrent glioblastoma and a PFS6 of 35.7% and a 1-year survival of 60.7% in recurrent anaplastic astrocytoma patients.[42] TMZ with both the dose-dense (dd) and metronomic (mn) schedules showed promising responses in recurrent high grade glioma patients. However, the superiority of either dosing schedule hasn't been established and comparison within the same clinical trial setting is therefore warranted.

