3 STUDY IMPLEMENTATION

3.1 STUDY DESIGN:

3.1.1 Phase I:

The phase I component is designed to find the MTD of Zotiraciclib (TG02) in combination with 2 schedules of TMZ – dose dense and metronomic. Patients will be enrolled and equally assigned into the two dosing schedule arms for MTD finding. In each arm, the MTD will be determined independently using the Bayesian Optimal Interval (BOIN) design, fully described in Section 8 and recently published [45]. Once the MTDs of the two regimens (dd TMZ + Zotiraciclib (TG02) and mn TMZ + Zotiraciclib [TG02]) have been established, cohort expansion will be carried out at the each of the MTDs. Patients will be equally randomized into to the two cohort expansions. A post interim analysis cohort will be carried out in cohort 1 arm 1 to confirm MTD. The MTD that has higher progression-free survival rate at 4 months (PFS4) will be selected and used in phase II.

3.1.2 Phase II:

The two-arm randomized phase II will determine if the addition of Zotiraciclib (TG02) to the dd or mn TMZ schedule (determined by the expanded phase I) improves outcome in patients with recurrent malignant glioma using PFS as the primary outcomes measure. Patients will be equally randomized into the combination Arm (Zotiraciclib [TG02] plus TMZ selected from phase I) and control arm (TMZ). The randomization will stratify by the presence of measurable disease at the study entry, KPS and MGMT promoter methylation status. Additional outcomes such as PFS6, overall survival from study entry and symptom burden (using the MDASI-BT instrument in Appendix **Error! Reference source not found.**) will also be collected.

The study schema is illustrated in Study Flow Chart in Appendix 15.4.

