A randomized phase II trial will be used to compare the combination of Zotiraciclib (TG02) plus TMZ (selected from phase I) with TMZ alone in patients with recurrent grade III or IV malignant glioma. The TMZ alone arm will use the same dosing schedule as it is in the combination arm. The primary endpoint is progression free survival. We will enroll at least 10 patients and at most 40 patients for each arm at a rate of 4 patients per month. Patients will be equally randomized into two arms. Patients' KPS, MGMT promoter methylation status of the tumors and the presence of measurable disease at study entry will be used as stratification factors. We will follow all patients for at least 12 months, and monitor futility and toxicity as described below. We will use the methods described by Thall et al., to monitor progression-free survival (PFS), and we will stop enrolling patients early if, based on the available data, we have reason to believe that the median PFS of the Zotiraciclib (TG02) plus TMZ arm is less than that of the TMZ arm.^[50] Formally, we will stop enrolling patients early if

$$\Pr(\text{median PFS}_{\text{TG02+TMZ}} \geq \text{median PFS}_{\text{TMZ}} \mid \text{data from the trial}) < 0.78,$$

The futility monitoring will be conducted after enrolling 20, 40 and 60 patients (for two arms combined). Below are the operating characteristics of the above futility monitoring rule, assuming that the median PFS of the TMZ alone arm is 3 months.

Table 15 Operating Characteristics of the Futility Monitoring rule

	Median PFS for Zotiraciclib (TG02) +TMZ (months)				
	1	2	3	4	5
Early stop probability	0.999	0.812	0.374	0.170	0.097
Average sample size	23.7	42.1	62.6	70.9	74.7

Similar Bayesian methods will also be used to monitor the rate of DLT. We will monitor the two arms independently. Specifically, we will stop enrolling patients if the $\Pr(\text{DLT} > 35\% \mid \text{data}) > 0.9$. That is, we will stop enrolling patients if the data indicate that there is more than 90% chance that the true DLT rate is higher than 35%. This decision rule gives the following stopping rule, assuming a Beta (0.1, 0.4) prior distribution for DLT rate,

Stop enrolling pts if $[\# \text{ of pts with DLT}] / [\# \text{ of pts evaluated}] \geq 4/5, 6/10, 10/20, \text{ and } 15/30$.

Below are the operating characteristics of the toxicity monitoring rule.

Table 16: Operating Characteristics of the Toxicity Monitoring Rule

	True toxicity rate				
	0.2	0.3	0.4	0.5	0.6

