Early stop probability	0.014	0.096	0.345	0.716	0.939
Average sample size	39.6	37.3	31.0	21.3	13.5

At progression, patients on the control arm will be offered treatment with Zotiraciclib (TG02) in combination with continued treatment with TMZ. If an effective salvage regimen, this may impact the secondary OS endpoint, but will not affect the primary endpoint of the study. The maximum number is 80 patients.

Statistical Analysis Plan

We will use descriptive statistics to summarize the demographic and clinical characteristics of patients. We will tabulate adverse events by grade by dose level and overall. For the cohort expansion and phase II component, we will estimate the proportion of patients with response with 95% exact binomial confidence intervals, and use descriptive statistics to summarize response duration. We will estimate PFS/OS with the Kaplan-Meier product limit estimator. Log-rank test will be used to compare the PFS/OS between Zotiraciclib (TG02)+TMZ and TMZ.

Changes of symptom burden (i.e., MDASI-BT) through study time points will be assessed by paired t-tests and linear mixed model. In the mixed model, subject-specific random intercept will be used to account for within-subject correlation, and measurement time will be included as a covariate. A sample size of 40 patients has 80% power to detect an effect size of 0.454 between time points using a two-tailed test with an alpha of 0.05. The two-sample t-test and linear mixed model will be used to evaluate differences in symptom burden using the MDASI-BT between Zotiraciclib (TG02) plus TMZ and TMZ. Cox proportional hazard model will be used to evaluate the relationship between MDASI-BT and disease progression. Logistic regression will be used to evaluate the relationship between MDASI-BT and tolerance to treatment.

Treatment effects will be evaluated by advanced MRI imaging study. Perfusion and diffusion – based MRI parameters, including but not restricted to blood volume, blood flow mean and median Apparent Diffusion Coefficient (ADC) value will be analysed. Results will be summarized. The mean and median value at different time points will be tabulated. Changes in such parameters will be analysed for statistical significance and correlate with the disease status.

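### Phase II pools WHO grade III and IV astrocytoma but leaves grade out of both the stratification and the PFS/OS comparison; a grade-stratified analysis would remove the effect of chance imbalance, modest for PFS and larger for OS

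*Combined protocol and SAP*

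**What the plan says.** The phase II population is defined in section 10.2 as patients "in patients with recurrent grade III or IV malignant glioma". Section 2.1.1 admits both grades and caps neither.

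Three places list the stratification factors, and they agree: KPS, MGMT methylation and measurable disease. These are the table in 2.3.1, section 3.1.2 ("The randomization will stratify by the presence of measurable disease at the study entry, KPS and MGMT promoter methylation status") and section 10.2 ("MGMT promoter methylation status of the tumors and the presence of measurable disease at study entry will be used as stratification factors"). WHO grade is in none of them.

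The Statistical Analysis Plan part of 10.2 states: "Log-rank test will be used to compare the PFS/OS between Zotiraciclib (TG02)+TMZ and TMZ". No strata or covariates are named. The only Cox model serves another purpose: "Cox proportional hazard model will be used to evaluate the relationship between MDASI-BT and disease progression". The futility rule compares the two arm medians and takes one control median of 3 months for both grades. No subgroup or sensitivity analysis by grade appears.

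On prognosis, section 1.2.1 describes anaplastic astrocytoma as "demonstrating a less aggressive behavior when comparing to GBM". Section 1.2.6 cites one metronomic TMZ study that "yielded a PFS6 of 23.9% and a 1-year survival rate of 27.3% in recurrent glioblastoma", against 35.7% and 60.7% in recurrent anaplastic astrocytoma.

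**The concern.** Grade is known before entry for every patient, and the protocol's own background treats it as prognostic. Leaving it out of both allocation and analysis means the arms can differ in grade mix by chance, with nothing in the planned comparison to account for it. With at most 40 patients per arm, and 10 per arm at the first futility look, some imbalance is to be expected. At stake are the estimated treatment effect in this one trial, above all for OS, and some precision. If an imbalance appears, an adjustment chosen after seeing it would be open to challenge.

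**Working it through.** **Plan's own figure.** Table 15 is the only operating characteristic given for the phase II PFS comparison; no alpha, power or target hazard ratio is stated for the log-rank test. I simulated the rule with exponential PFS, looks at 20, 40 and 60 patients, 4 patients per month, and an assumed weak inverse-gamma prior (shape 2, scale 3/ln 2), since the prior is not given.

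| Early-stop probability at combination median (months) | 1 | 2 | 3 | 4 | 5 |
|---|---|---|---|---|---|
| Table 15 | 0.999 | 0.812 | 0.374 | 0.170 | 0.097 |
| Printed cutoff 0.78 | 1.000 | 0.993 | 0.934 | 0.791 | 0.661 |
| Cutoff 0.22 | 1.000 | 0.814 | 0.365 | 0.169 | 0.088 |

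The table fits 0.22, not the printed 0.78. That is a separate matter on which this point does not depend; 0.22 is used for the futility illustration below.

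**Step 1: grade hazard ratios.** Under exponential survival, HR (III:IV) = ln S(III) / ln S(IV), with the rates in section 1.2.6:
- PFS: ln 0.357 / ln 0.239 = 1.030 / 1.431 = 0.72 (IV:III 1.39).
- OS: ln 0.607 / ln 0.273 = 0.499 / 1.298 = 0.38 (IV:III 2.60).
- PFS with the pooled anaplastic astrocytoma PFS6 of 31% from section 1.2.1: ln 0.31 / ln 0.239 = 1.171 / 1.431 = 0.82. This crosses studies.

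**Step 2: chance imbalance.** The documents give no grade mix, so I assumed 10% to 50% grade III and took two independent binomials, with no credit for balance gained indirectly through the other factors.

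| Gap between arms | 30% grade III | Range over 10-50% |
|---|---|---|
| 20 points or more, 10 per arm | 46% | 24-50% |
| 20 points or more, 20 per arm | 23% | 6-27% |
| 20 points or more, 40 per arm | 7% | 0.5-9% |
| 10 points or more, 40 per arm | 39% | 19-43% |

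**Step 3: effect on the hazard ratio.** To first order the log HR shifts by gap × ln(IV:III hazard ratio).
- PFS, 20 points: exp(0.20 × ln 1.39) = 1.07, or 1/1.07 = 0.94 in the other direction. Simulated slopes of 0.34-0.38 give 1.07-1.08. Hence about 6-8%.
- OS, 20 points: exp(0.20 × ln 2.60) = 1.21. Simulated slopes of 0.89-1.03 give 1.20-1.23. Hence 20-23%.
- PFS at the 0.82 value, 20 points: exp(0.20 × ln(1/0.82)) = 1.04, about 4%.

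For scale, if all 80 patients had events, the standard error of the log HR would be about 2/√80 = 0.22. A 20-point gap shifts log HR by about 0.07 for PFS, a third of that, and by 0.18-0.21 for OS, close to one.

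**Step 4: stratified against unstratified log-rank.** Simulation with 40 per arm, at least 12 months of follow-up and a two-sided 5% test:
- No treatment effect: rejection 5.2-5.8% unstratified and 5.4-6.1% stratified.
- Dependence on the grade gap: the stratified slope is near zero (-0.07 to +0.02).
- PFS power at an assumed treatment HR of 0.6: 56-58% either way.
- OS power at the same HR and 30% grade III: from about 42-43% to 47-49%. Over 15-50% grade III: 38-47% to 44-50%.

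**Step 5: first futility look.** With no treatment effect, PFS grade HR 1.39 and cutoff 0.22, the stop probability is 0.20 with 7 of 10 grade IV in each arm. It becomes 0.24 with 9 (combination) against 6 (control), and 0.16 with 5 against 8.

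**The case against.** The strongest reply is that randomisation already protects validity and that the primary endpoint gains almost nothing. That stands: type I error is near nominal, PFS power does not change at a grade HR of 0.72, and a 20-point gap at full size is unlikely. Section 1.2.1 also gives a pooled median PFS of 13 weeks in recurrent anaplastic astrocytoma, about the 3-month control median assumed in 10.2, so the PFS gap by grade may be smaller than 0.72 suggests. If the general incidence shares in 1.2.1 applied (7 / (54 + 7) = 11% anaplastic astrocytoma), imbalance would sit near the low end of the range.

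The larger effect is on OS, which is secondary and which 10.2 already says crossover may affect. The rates in 1.2.6 come from the metronomic schedule, while 10.1 names dose-dense as the winner. Three binary factors already make 8 cells for at most 80 patients, and a fourth makes 16, so omitting grade from the allocation is a defensible trade-off. MGMT and KPS may balance grade in part, though the documents give no figure.

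None of this gives a reason to leave grade out of the analysis, where it adds no data and little cost.

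A reader might infer more than the documents support:
- That the arm with more grade III will look better whatever the drug does. A 6-8% shift in the PFS hazard ratio does not override a sizeable real effect.
- That the grade HR for PFS is as strong as 0.54, from the PFS6 of 46% in 1.2.1 against 23.9%. That contrast crosses studies, and 1.2.6 itself cites two dose-dense studies in similar patients with PFS6 of 43.8% and 10%.
- That the futility looks are badly distorted. Step 5 shows a shift of about 4 percentage points for a 30-point gap.

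**Conclusion.** The concern holds as a matter of efficiency and robustness. Grade is prognostic on the protocol's own figures, and the plan accounts for it in neither the allocation nor the comparison. The consequence is a possible shift in one trial's estimate, modest for PFS and larger for OS, plus a few points of OS power. It is not a bias and not an inflated error rate, and a reader who took the plan to be invalid on this ground would be going beyond the documents.

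The size rests on exponential survival, grade hazard ratios from one cited study on the metronomic schedule, an assumed 10-50% grade III share, an assumed treatment HR of 0.6, and no indirect balancing through MGMT or KPS. A weaker grade effect on PFS, as the pooled figure in 1.2.1 suggests, would make the PFS consequence smaller still.

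**What to change.** In 10.2, pre-specify that the PFS and OS comparisons use a log-rank test stratified by WHO grade (III or IV), or a Cox model with a grade term, and say which of the two is primary. Use the grade confirmed centrally before entry (2.1.1.1 and 2.2.4). Because 2.2.4 accepts tissue from the initial or the recurrent disease, and 1.2.1 notes that anaplastic astrocytoma often transforms to glioblastoma, state which specimen defines grade when both exist.

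Adding grade to the randomisation in 2.3.1, 3.1.2 and 10.2, for example by minimisation to avoid 16 small cells, or to the futility model, is optional.

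The cost is a few lines of text and slightly more analysis work, with no new data. The main downside is that the grade III stratum may be small and then contribute little information.
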